8. DATA QUALITY ASSURANCE

8.1. Clinical Procedures

Sponsor personnel or designee(s) will visit the study site if necessary prior to initiation of the study to review information about the study drug, protocol requirements, eCRFs, monitoring requirements, reporting of serious adverse events, and to ensure a full understanding of the Study Reference Manual with the site personnel.

8.2. Monitoring

This study will be monitored by the sponsor (or designee) in accordance with current Good Clinical Practice (GCP) regulations. By signing this protocol, the investigator grants permission to Myovant Sciences GmbH (or designee) and appropriate regulatory authorities to conduct on-site monitoring of all appropriate study documentation. In order to assure the accuracy of data collected in the eCRF, it is mandatory that representatives of the sponsor (or designee) have access to original source documents (eg, patient records, patient charts, and laboratory reports). During the review of these documents, the anonymity of the patient will be respected with strict adherence to professional standards of confidentiality. A study monitor will contact and visit the site regularly and will be allowed, on request at a mutually acceptable time, to inspect the various records of the study. It will be the study monitor's responsibility to inspect the eCRF at regular intervals throughout the study, to verify the adherence to the protocol and the completeness, correctness and accuracy of all eCRF entries, and to meet with the investigator to discuss study progress and compliance with the protocol and GCP. The study monitor should have access to laboratory test results and any other source records and data needed to verify the entries on the eCRF. The investigator agrees to cooperate with the study monitor to ensure that any problems detected in the course of these monitoring visits are resolved. For this study, patient data will be entered into a sponsor-approved electronic database and combined with data provided from other sources in validated datasets then transmitted electronically to the sponsor (or designee).

Management of clinical data will be performed in accordance with applicable sponsor-approved standards and data cleaning procedures to ensure the integrity of the data (eg, removing errors and inconsistencies in the data).

Adverse events and concomitant medications terms will be coded using the Medical Dictionary for Regulatory Activities (MedDRA) and the World Health Organization Drug Dictionary Enhanced, respectively.

The investigator will retain original source documents and the sponsor will receive eCRF-required data as electronic datasets. Patient initials will not be collected or transmitted to the sponsor.

9. STATISTICAL CONSIDERATIONS AND DATA ANALYSES

A statistical analysis plan (SAP) will describe the detailed statistical methods and analyses for this study. The SAP will be prepared and finalized prior to unblinding of patients' study treatment assignments.

All hypothesis tests and confidence intervals will be 2-sided at an alpha level of 5%. Methodology to be used to maintain study-wide type I error rate of 5% across primary and secondary endpoint testing will be described in the SAP.

All efficacy and safety measures over the course of the study will be presented. Continuous data will be summarized by means, standard deviations, medians, maximum, minimum, and number of patients. Categorical data will be summarized by counts and percentages.

9.1. Randomization Methods

Central randomization will be used and treatment allocation will be 1:1:1 to relugolix plus low-dose hormonal add-back therapy (Group A), relugolix monotherapy plus placebo followed by relugolix plus low-dose hormonal add-back therapy (Group B), and placebo (Group C).

Randomization will be stratified by the following factors:

- Geographic Region: North America versus Rest of World; and
- Mean screening menstrual blood loss using alkaline hematin method: < 225 mL versus \geq 225 mL.

Statistical analyses for all efficacy endpoints will incorporate these stratification factors unless otherwise specified.

9.2. Analysis Populations

The Intent-to-Treat (ITT) Population will consist of all patients randomized to treatment who have taken at least one dose of study treatment. This will be the primary population used for the efficacy analysis.

The Per-Protocol Population will consist of those members of the ITT Population who have no relevant major protocol violations, defined as a subset of all major protocol violations (details will be provided in the statistical analysis plan). The Per-Protocol Population will not be analyzed if this population comprises more than 95% or less than 50% of the ITT Population.

This population will be used for confirmatory analysis of the primary efficacy endpoint. The Per-Protocol Population will be identified prior to breaking the study blind.

The primary population for safety analyses will be the Safety Population, which will consist of all patients who are randomized and took at least one dose of study treatment.

9.3. Efficacy Analyses

Inferential efficacy assessments will be made between the following groups and 24 Weeks of placebo:

- Relugolix Group A: 24 weeks of oral relugolix 40 mg once daily co-administered with low-dose estradiol and norethindrone acetate;
- Relugolix Group B: 12 weeks of oral relugolix 40 mg once daily followed by 12 weeks of oral relugolix 40 mg once daily co-administered with low-dose estradiol and norethindrone acetate.

Descriptive characterization of treatment effect will be assessed between both relugolix groups.

9.3.1. Primary Endpoint Analysis

The primary endpoint is the proportion of women in the relugolix Group A versus the placebo Group C who achieve both a menstrual blood loss volume of < 80 mL AND at least a 50% reduction from baseline in menstrual blood loss volume over the last 35 days of treatment as measured by the alkaline hematin method.

Baseline menstrual blood loss is defined as the average menstrual blood loss from the two Screening menstrual cycles used to meet the inclusion criteria prior to the date of the first dose of study drug as assessed by the alkaline hematin method. The menstrual blood loss during the final study month is the total menstrual blood loss during the last 35 days on treatment as assessed by the alkaline hematin method. The treatment comparison between the relugolix Group A and the placebo Group C will be analyzed using a Cochran-Mantel-Haenszel test statistic for stratified proportions. The differences between the relugolix Group A and placebo Group C and 2-sided 95% confidence intervals will be estimated based on stratum-adjusted Mantel-Haenszel proportions.

Patients who discontinue the study before Week 4 (28 days) will be considered as treatment failures for the primary endpoint. The primary analyses will be based on the ITT Population. In addition, analyses of the Per-Protocol Population will be used to support the primary efficacy analysis. Details will be provided in the SAP. Additional missing data imputations will be conducted as sensitivity analyses to support the primary analysis. Details will be provided in the SAP.

For the assessment of the superiority of relugolix Group A versus placebo Group C in the proportion of patients who achieve both a menstrual blood loss volume of < 80 mL AND at least a 50% reduction in menstrual blood loss volume over the last 35 days of treatment, a sample size of ~130 patients in the relugolix Group A versus ~130 in the placebo Group C will provide greater than 99% power to detect a difference of greater than 30% using a 2-sided test at

significance level of 0.05. The study will enroll 3 groups with a targeted 130 patients in each group for a total sample size of 390.

9.3.2. Secondary Endpoint Analyses

The secondary endpoints are listed below:

- Proportion of women in the relugolix Group B versus the placebo Group C who achieve a menstrual blood loss volume of < 80 mL AND at least a 50% reduction from baseline menstrual blood loss volume over the last 35 days of treatment, as measured by the alkaline hematin method.

The following secondary endpoints will be assessed comparing each relugolix treatment group to placebo inferentially and relugolix Group A to Group B descriptively:

- Time to achieving a menstrual blood loss volume of < 80 mL AND at least a 50% reduction from baseline menstrual blood loss volume as measured by the alkaline hematin method;
- Change from Baseline to Week 24 in menstrual blood loss;
- Proportion of women who achieve amenorrhea over the last 35 days of treatment;
- Proportion of women with a hemoglobin below the lower limit of normal at Baseline who achieve an increase of ≥ 1 g/dL from Baseline at Week 24;
- Change from Baseline to Week 24 in impact of uterine fibroids based on the UFS-QOL activities domain;
- Change from Baseline to Week 24 in the interference of uterine fibroids with physical activities based on UFS-QOL Question 11;
- Change from Baseline to Week 24 in the interference of uterine fibroids with social activities based on UFS-QOL Question 20;
- Change from Baseline to Week 24 in embarrassment caused by uterine fibroids based on UFS-QOL Question 29;
- Change from Baseline to Week 24 in uterine fibroid-related symptoms based on the Uterine Fibroid Scale – Symptom Severity;
- Change from Baseline to Week 24 in uterine fibroid-related quality of life based on the Uterine Fibroid Scale – Health-related Quality of Life;
- Change in PGA for uterine fibroid related function from Baseline to Week 24;
- Change in PGA for uterine fibroid symptoms from Baseline to Week 24;
- Change from Baseline to Week 24 in the Menorrhagia Impact Questionnaire Score for physical activities;
- Change from Baseline to Week 24 in the Menorrhagia Impact Questionnaire Score for social and leisure activities;
- Proportion of women who achieve a mean Numerical Rating Scale score for uterine fibroid-associated pain over the last 35 days of treatment that is at least a 30% reduction from Baseline in the subset of women with a maximum pain score ≥ 4 during the 35 days prior to randomization;
- Change from Baseline to Week 24 in uterine volume; and

- Change from Baseline to Week 24 in uterine fibroid volume.

The analysis methods used for the primary endpoint will be applied to the analyses of the secondary endpoints of proportion of patients who achieve both a menstrual blood loss volume of < 80 mL AND at least a 50% reduction in menstrual blood loss volume over the last 35 days of treatment compared between relugolix Group B and placebo Group C, the proportion of patients with amenorrhea over the last 35 days, the proportion of women with a hemoglobin below the lower limit of normal at Baseline who achieve an increase of at least 1 g/dL at Week 24 and the proportion of women who achieve a mean Numerical Rating Scale score for uterine fibroid-associated pain over the last 35 days of treatment that is at least a 30% reduction from Baseline in the subset of women with a maximum pain score ≥ 4 during the 35 days prior to randomization.

For the secondary endpoints of time to achieving a menstrual blood loss volume of < 80 mL AND at least a 50% reduction from baseline menstrual blood loss volume, time to event will be defined as weeks from randomization to first occurrence of the event as assessed by the alkaline hematin method. Patients without an event will be censored at last assessment date prior to the end of study. Kaplan-Meier methods will be used to describe the time to event distributions and stratified log-rank test will be used to compare each relugolix arm to placebo. Randomization stratification factors will be used to stratify inferential testing.

Descriptive statistics will be provided for changes in menstrual blood loss, hemoglobin, UFS-QOL score, PGA for function and symptoms, MIQ Score, Numerical Rating Scale score for uterine fibroid-associated pain, uterine volume, and uterine fibroid volume baseline. The between treatment comparisons will be performed using model derived least squares means with treatment, stratification factors, baseline result accounted for in the model.

Baseline Numerical Rating Scale score is defined as the average Numerical Rating Scale score from the 35 days of data collected prior to the date of first dose of study drug after randomization. The Numerical Rating Scale score during the final study month is the average Numerical Rating Scale score during the last 35 days on treatment.

Details on the endpoint analyses including derivations, handling of missing data, and statistical methods will be provided in the SAP.

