
Efficacy
 
The efficacy analyses will be conducted using an Intent-to-Treat (ITT) Population defined as all randomized patients, unless otherwise specified in the statistical analysis plan. Randomization will be 1:1:1 with the stratification variables of geographic region and mean screening menstrual blood loss volume (mL per alkaline hematin method) as follows:
 
 • Geographic Region: North America versus Rest of World; • Mean screening menstrual blood loss volume: < 225 mL versus \geq 225 mL. 
The randomization stratification factors will be incorporated into inferential testing of all efficacy endpoints, unless otherwise specified.
 
The primary hypothesis tested in this study is whether relugolix co-administered with 1.0 mg estradiol and 0.5 mg norethindrone acetate is superior to placebo in the percentage of women who achieve both a menstrual blood loss volume of < 80 mL AND at least a 50% reduction in menstrual blood loss volume over the last 35 days on treatment as compared with Baseline.
 
The point estimate and 2-sided 95% confidence interval of the difference in the proportion will be calculated between the relugolix Group A and placebo Group C. The between-treatment comparisons will be performed using the Cochran-Mantel-Haenszel method.
 
The comparisons of the relugolix arms versus placebo will be performed for the secondary efficacy and safety endpoints using appropriate statistical methods. Comparisons between the two relugolix arms will be descriptive. A closed testing procedure will be used to control the overall type I error rate of 5% across primary and secondary endpoint testing. Details of this procedure will be provided in the statistical analysis plan.
 
Sample Size
 
Assuming a placebo control response rate of 25%, the assessment of the superiority of relugolix 40 mg co-administered with low-dose hormonal add-back therapy (Group A) versus placebo (Group C) in the proportion of patients who achieve both a menstrual blood loss volume of < 80 mL AND at least a 50% reduction in menstrual blood loss volume over the last 35 days of treatment, a sample size of 260 (130
	

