patients in each of the relugolix and placebo arms) will provide > 99% power to detect a difference of greater than 30 percentage points using a 2-sided test at significance level of 0.05. The total sample size for the study will be approximately 390 patients (130 patients in each of the 3 arms).

Safety

Safety assessments will include treatment-emergent adverse events, vital signs, physical examinations, clinical laboratory tests, 12-lead electrocardiograms, endometrial biopsies, and assessments of bone mineral density. Safety analyses will be based on all randomized patients who receive any amount of study drug (safety population). Drug exposure will be summarized by descriptive statistics. Severity of all treatment-emergent adverse events will be evaluated by the investigator based on the National Cancer Institute's Common Terminology Criteria for Adverse Events (CTCAE) and will be coded to preferred term, higher level term, and system organ class using the Medical Dictionary for Regulatory Activities (MedDRA). The number and percentage of patients with adverse events will be presented by MedDRA system organ class and preferred term, relationship to study drug, and severity. Descriptive statistics will be used rather than inferential statistics. Laboratory values also will be classified by toxicity grade based on the National Cancer Institute's CTCAE. Laboratory shift tables of the Baseline results to each of the subsequent visits will be produced. Bone mineral density will be evaluated in all patients at the lumbar spine (L1-L4), total hip, and femoral neck at the Baseline, Week 12, and Week 24 visits and the absolute, percent, and standardized changes from baseline will be summarized.

Vasomotor adverse events will be separately summarized.

A chartered independent Data and Safety Monitoring Board will monitor all available safety data, including bone density assessments, on an ongoing basis during this study.

Pharmacokinetics and Pharmacodynamics

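### The hemoglobin responder endpoint is tested without baseline hemoglobin in the analysis: valid, but it probably gives away some precision that one pre-specified model would recover

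*Protocol*

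**What the plan says.** Protocol Section 9.3.2 lists four responder-type secondary endpoints by name, the hemoglobin endpoint among them, and says of them: "The analysis methods used for the primary endpoint will be applied to the analyses of the secondary endpoints". Section 9.3.1 defines the primary method: the comparison "will be analyzed using a Cochran-Mantel-Haenszel test statistic for stratified proportions", with differences and intervals from stratum-adjusted Mantel-Haenszel proportions. Section 9.1 sets the strata as region (two levels) and mean screening menstrual blood loss (two levels, cut at 225 mL).

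For continuous changes, Section 9.3.2 instead uses "least squares means with treatment, stratification factors, baseline result accounted for in the model".

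Baseline hemoglobin is available. The Schedule of Activities (Section 1.1, footnote j) includes a complete blood count at every laboratory visit, Baseline Day 1 among them, and Table 6-1 lists hemoglobin within it. The endpoint's subset is itself defined by the baseline value.

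The protocol gives no size for this subset, no responder rate in it and no power for it. Its only sample-size statement concerns the primary endpoint in all randomized women.

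**The concern.** The responder outcome is a change from baseline cut at 1 g/dL. Section 9.3.2 treats the baseline value as worth adjusting for when a change is analysed as it stands, but not when this change is dichotomized, and it gives no reason.

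Two features of the design suggest that starting hemoglobin is prognostic here. Women are selected for a low value, so regression to the mean favours larger rises from lower starts. Section 5.10.2.2 also requires iron therapy for microcytic iron deficiency anemia with hemoglobin from 8 to 10 g/dL, in all arms, and states no such requirement above 10 g/dL. Neither randomization stratum measures hemoglobin directly.

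At stake is the width of the interval and the power of one secondary comparison per relugolix group, made in a subset of the randomized women.

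**Working it through.** **1. The plan's own figure.** Inputs: 130 per arm (Section 9.3.1), 25% against 55%, two-sided 0.05 (Synopsis). With pooled rate 0.40,

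z = [0.30·√130 − 1.96·√(2·0.40·0.60)] / √(0.25·0.75 + 0.55·0.45) = (3.421 − 1.358) / 0.660 = 3.13, so power is 99.9%.

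The statement that the sample "will provide > 99% power to detect a difference of greater than 30 percentage points using a 2-sided test at significance level of 0.05" is reproduced. It says nothing about the hemoglobin subset.

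**2. What subset size would mean (assumed shares and rates).** Unadjusted power:

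| Share of 130 | n per arm | 20% vs 40% | 20% vs 50% |
|---|---|---|---|
| 20% | 26 | 0.35 | 0.63 |
| 30% | 39 | 0.49 | 0.81 |
| 50% | 65 | 0.71 | 0.96 |
| 70% | 91 | 0.84 | 0.99 |

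Whether precision is scarce depends on numbers the protocol does not state.

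**3. Gain from adjustment, large-sample formula.** Assumptions, none from the protocol except the floor of 8 g/dL: baseline H between 8 and 12 g/dL; mean change 1.3 (relugolix) and 0.3 (placebo); residual SD 1.1; slope β of change on baseline. The response probability in arm t is m_t(H) = Φ{[μ_t − 1 + β(H − mean H)] / 1.1}. With equal allocation the proportional fall in variance is

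ρ = Var(m₁ + m₀) / {2[p₁(1−p₁) + p₀(1−p₀)]},

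and the gain in effective patients is 1/(1−ρ) − 1.

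Example: H uniform on 8 to 12 has SD 4/√12 = 1.155. At β = −0.5 the share of variance in the continuous change explained is 0.333/(0.333 + 1.21) = 0.216. After dichotomizing, ρ = 0.138, and the gain is 1/0.862 − 1 = 16%.

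| β | H uniform (SD 1.155) | H normal(11.2, 1.2) cut to 8–12 (SD 0.85) |
|---|---|---|
| 0 | 0% | 0% |
| −0.3 | 5.8% | 3.1% |
| −0.5 | 16.0% | 8.6% |
| −0.7 | 31.1% | 16.5% |

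**4. Simulation of both analyses, 30 to 80 per arm.** One set of runs (4,000 replicates, baseline 8 to 12 g/dL) gave 8–11% at −0.5 and 2–18% over −0.3 to −0.7. Another (1,500 replicates, uniform baseline) gave about 0% at slope 0, 3–6% at −0.3, 12–16% at −0.5 and 27–32% at −0.7. Step 3 shows that the assumed spread of baseline hemoglobin alone can produce a difference of this size. The risk difference was essentially the same under both analyses (about 0.31–0.34 in the first set).

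A third model, with log-odds slopes of 0, −0.3, −0.7 and −1.2 per g/dL and 39 or 65 per arm, gave variance ratios (adjusted to Mantel-Haenszel) of 1.00, 0.97–0.98, 0.93 and 0.82–0.85. The last equals 1/0.85 − 1 = 18% to 1/0.82 − 1 = 22% more patients.

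**5. Type I error of the adjusted analysis.** With an uncorrected robust Wald interval it was 6.6–7.1% at 30 per arm, 5.9–6.6% at 40 and 5.5–6.2% at 80, against 4.6–5.3% for Cochran-Mantel-Haenszel. A second set of runs gave 5.7–8.3% at 30 to 40 per arm, falling to about 4–6.5% with a degrees-of-freedom correction and a t reference.

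**6. Other responder endpoints.** The same exercise gave under 1% for the primary endpoint and 0.2% for the pain responder endpoint.

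**The case against.** The strongest reply is that nothing here is wrong. A stratified Cochran-Mantel-Haenszel analysis on the randomization factors is standard and valid. Section 9.1 applies those factors unless otherwise specified, and Section 9.3.2 leaves further statistical detail to the SAP, which was not available for this review and may add the covariate. Validity is conceded. But Section 9.3.2 does name the method for this endpoint, so it is a stated choice that can be improved.

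The reply also limits what a reader might infer:

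- That chance imbalance in hemoglobin biases the result. It does not. Randomization keeps the estimate unbiased on average, and its interval already allows for such imbalance. Only the width is affected.
- That this subset is small, or the smallest among the tested endpoints. No subset size is given, and the pain responder endpoint is also restricted to a subset.
- That baseline hemoglobin is shown to predict a rise. The protocol gives grounds to expect it but no slope, and the truncated range weakens any relation.
- That baseline hemoglobin is never used. On a plain reading, Section 9.3.2 also compares change in hemoglobin with baseline in the model, although that is not the listed secondary endpoint.

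Finally, a simple robust Wald interval from the adjusted model is anti-conservative in small samples (step 5). Part of any apparent power gain would then come from the test: with 39 per arm and slope 0, power rose by about 4 points with no gain in variance. This objection stands, and the fix must deal with it.

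**Conclusion.** This is an optional improvement in efficiency, not an error or a contradiction. The expected gain is nil if baseline hemoglobin is not prognostic, about 8 to 16% more effective patients at a slope of −0.5, and roughly 18 to 30% at −0.7. In interval width, 8 to 16% means about 4 to 7% narrower (1/√1.08 = 0.96; 1/√1.16 = 0.93).

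These figures rest on assumed values for the slope, the spread of baseline hemoglobin, the mean changes and the residual SD. The protocol supplies none of them, nor the subset size. The direction is well supported: in the simulations adjustment cost essentially no precision at slope 0 and gained some at every non-zero slope. The case is confined to hemoglobin, because the primary and pain responder endpoints showed no useful gain.

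**What to change.** Before unblinding, state in Section 9.3.2, and in the SAP, for the hemoglobin responder endpoint and for each relugolix group against placebo:

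- the estimate is a standardized (marginal) risk difference from a logistic model with treatment, the two randomization factors and continuous baseline hemoglobin;
- the interval and test use a robust variance with a degrees-of-freedom correction and a t reference;
- this is the one analysis whose p-value enters the closed testing procedure promised in the Synopsis;
- the Cochran-Mantel-Haenszel test and Mantel-Haenszel difference are reported as supporting.

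The cost is one extra model and no new data. The reported quantity remains a difference in proportions. The timing matters because a switch after unblinding would look data-driven. If the small-sample correction is left out, the interval will be slightly too narrow when the subset is small.
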